6.1 The Paediatric Familial Hypercholesterolaemia Register (PFHR)

NHS HRA REC reference: 23/NE/0035

See full protocol in section 14 (APPENDIX: Full Protocol for NHS HRA REC reference: 23/NE/0035)

Existing Register size and representativeness: The PFHR was established in 2012 with the primary aim of monitoring LLT safety nationally, and feeding back to clinics on routine care.^{9,10} Up to and including 2019, there are 613 patients registered on the PFHR from across 39 clinical sites in England. Using a secure web-based portal, the Register captures routine clinical and demographic data from specialist clinics seeing patients with paediatric FH. Children treated with LLT and those without LLT treatment are both well-represented on the PFHR.¹⁰ Age, gender and lipid profiles are similar to those reported in other child FH populations,²⁶ and 75% are of white ethnicity (compared with 86% of the national UK population). The mean age of diagnosis is 9 years (Standard deviation (SD) 4) with a mean follow-up of 2.9 years (SD 1.8) and 57% initiating LLT at some point (mean age of initiation is 11 years, SD 3). The Register has been dormant since 2019 due to lack of funding.

6.1.1 **Protocol summary for re-instating the Register**

This study will reinstate the Register and collect up to 3.5 further years of follow-up data, by consenting new paediatric FH patients and collecting both retrospective and prospective clinical follow-up data using routinely recorded information from clinic appointments. **Clinical data collection will maintain collection of the original Register data items with the addition of data items on LLT adherence, reasons for non-adherence, and patient-reported side-effects/intolerance**. New patient registration across all clinics will be promoted with a focus on funding recruitment and data entry time from clinical case notes at key clinical sites. These sites are in areas based on larger concentration of case numbers, socioeconomically, ethnically, and geographically diverse populations, and underserved urban communities (Manchester, Bristol, Harefield, Wessex, Nottingham, all 5 sites in South Wales, London).

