6.1.3 Inclusion criteria

- Age 0 years to 25 years (upper age limit can change in future based on data availability)
 Case recruitment is prioritised to the following:
 - a clinical or genetic diagnosis of FH (excluding confirmed homozygous, compound heterozygous/digenic FH)
 - age 7 years or older with a baseline cholesterol measurement (ideally at diagnosis) and planned clinical follow-up [based on current NICE guidelines for starting LLT by age 10, these children will have the opportunity to start LLT over the study duration]
 - o at least 1 available LDL-C measurement before age 16 years
 - o for cases on LLT, date treatment started and the pre-treatment LDL-C measurement
- Ability of participant with FH to provide informed consent at age 16 years or older
- Ability of participant's parent/guardian to provide informed consent for participants with FH under age 16 years
- Ability of participant with FH to provide informed assent at age 5-15 years for clinical data collection
- Attending a clinical site for their FH that has been approved for study recruitment

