6.4.1 Participant withdrawal

Participants will be free to withdraw (i.e., to stop completing the questionnaire or stop the interview) at any time without giving a reason. In addition, the research team may discontinue a participant's participation from the study at any time they consider it necessary for any reason including:

- Withdrawal of consent
- Incomplete/unusable data

When a participant withdraws from further participation, any information already obtained will be retained and may still be used in the final study analyses (this will be made clear in information sheets and consent forms).

7 Analysis

7.1 Objective 1: Estimate absolute and relative reductions in LDL-C, and in cumulative LDL-C, achieved in current practice with LLT, and whether these vary by age and LDL-C at initiation of LLT

Methods: We will evaluate the effectiveness of initiating LLT at different ages and LDL-C thresholds (at baseline) on LDL-C levels measured at **routine follow-up visits recorded in the PFHR** (and **secondarily in the CPRD FH population**). We will:

(a) estimate absolute and % reductions in LDL-C from pre-treatment levels, which will then be incorporated into the economic model,

(b) estimate cumulative LDL-C and time-weighted average (TWA) LDL-C, the latter providing an estimate of average LDL-C burden over childhood and adolescence,

(c) evaluate achievement of treatment targets, using expert-consensus recommendations for FH^{5,15} and average age-specific LDL-C levels in the general (non-FH) population (derived from CYP in the ALSPAC cohort),

(d) address potential evidence gaps by updating our current systematic review of statin trials in children with FH² to include all LLT and a new pragmatic review of high-quality observational evidence.

Analysis (a): **Absolute (mmol/L) and % reductions in LDL-C** from pre-treatment levels associated with age and LDL-C at LLT initiation will be estimated using a linear mixed-effects model. A multi-level structure will be used to account for children being grouped at clinical sites, with site as a random effect.

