LDL-C changes in those exposed to LLT will be compared with changes in those never exposed or unexposed up to a certain age, measured as the difference between the earliest and later follow-ups. We will use inverse probability of treatment weighting techniques^{28,29} to balance exposed and unexposed groups according to both baseline and time-varying measured confounders: family history of CVD and/or FH in family, gender, genetic testing, body mass index (BMI), ethnicity, other health conditions, reasons for not being on LLT or non-adherence, process factors such as attendance frequency, and socioeconomic deprivation (using post-code linkage to index of multiple deprivation).

We will primarily estimate intention-to-treat effects, i.e. the effect of prescribing LLT to children with FH on LDL-C levels.³⁰ We will then estimate per-protocol effects, which corresponds to the effect of continuously taking LLT during the following period. Potential treatment non-adherence and loss to follow-up will be accounted for via censoring weights.³⁰ Missing data in both the LDL-C outcomes and confounders will be addressed using multiple imputation.

We will conduct sensitivity analyses to assess the extent to which the effects of age and LDL-C at initiation are robust to potential unmeasured confounding. We will adopt the E-value approach,³¹ which essentially explores how strong (association with both LLT initiation and LDL-C outcomes) the unmeasured confounders need to be to change the study conclusions. These analyses will be informed by discussions with clinical specialists and PPIE groups, and the HCP questionnaire.

This will be a descriptive analysis with the ultimate aim to derive effectiveness estimates that will feed into the cost-effectiveness model, where uncertainty will be fully propagated.³² However, initial assessment, based on pre- and post-puberty in current PFHR data shows children initiating LLT before age 12 years achieved a mean reduction in LDL-C of 2.199 after initial mean levels of 6.115 (pooled SD=2.51) and those initiating LLT at 12 or older achieved a mean reduction in LDL-C of 1.748 after initial mean levels of 5.570 (pooled SD=1.53). Demonstrating this difference at 90% power and 0.05 significance level with a 60-40 allocation ratio (as in the current Register) would require 560 children initiating LLT before age 12 and 376 initiating LLT at 12 or older, which is within our planned recruitment target.

Secondary analyses:

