If insecure access to the REDCap consent, clinical or questionnaire data entry web interfaces was discovered from an external unauthorised source, the REDCap data entry interface would be suspended until methods of access were deemed secure.

Due to the nature and use of the data that is due to be collected as part of this study, there is no criterion for terminating the study.

ANALYSES

Methods

Statistical support for appropriate monitoring of study participant numbers, data completeness, data quality and the interview sampling frame will be provided by the Study Statistician at the

Page 21 of 37

Paediatric FH Register Study Protocol IRAS ID: 324246 18 June 2024 Final version 2.0

University of Nottingham with oversight of the Study Leads. Monitoring and analysis protocols will also be shared with the SSC and DMEC for their review.

Quantitative analyses will be conducted using Stata and R software by researchers with epidemiological, statistical and health economics expertise. Qualitative analyses will be conducted using NVivo software by researchers with qualitative methodology and analysis expertise.

Clinical effectiveness analysis

For the primary assessment of clinical effectiveness, absolute (mmol/L) and percentage reductions in LDL-C from pre-treatment (LLT) concentration levels will be estimated using a linear mixed-effects model. A multi-level structure will be used to account for patients being grouped at clinical sites, with site as a random effect. LDL-C changes in those exposed to LLT will be compared with changes in those never exposed or unexposed up to a certain age, measured as the difference between the earliest and later follow-up measurements. We will use the inverse probability of treatment weighting techniques¹⁵ to balance exposed and unexposed groups according to both baseline, and time-varying measured confounders: family history of CVD and/or FH in the family, gender, genetic testing, body mass index (BMI), ethnicity, other health conditions, smoking status, socioeconomic deprivation (using post-code mapped to index of multiple deprivation), reasons for not being on LLT or non-adherence, process factors such as attendance frequency.

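### The LDL-C change that is compared runs from the earliest follow-up, not from LLT start, although the stated target is reduction from pre-treatment levels, and comparators have no matching time zero

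*Protocol*

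**What the plan says.** Section 7.1 sets out to "estimate absolute and % reductions in LDL-C from pre-treatment levels" and carries the result into the economic model. Analysis (a) repeats the reference point: reductions "from pre-treatment levels associated with age and LDL-C at LLT initiation will be estimated using a linear mixed-effects model". The next step is the comparison: "LDL-C changes in those exposed to LLT will be compared with changes in those never exposed or unexposed up to a certain age", and that change is "measured as the difference between the earliest and later follow-ups". The Clinical effectiveness analysis in the appendix protocol has the same definition: "measured as the difference between the earliest and later follow-up measurements". No other operational definition of the compared change is given.

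The inclusion criteria (section 6.1.3, repeated in the appendix) prioritise children "with a baseline cholesterol measurement (ideally at diagnosis"), and ask separately, for treated cases, for the LLT start date and the pre-treatment LDL-C. So the protocol itself treats the diagnosis value and the pre-treatment value as two items. Section 6.1 describes the existing Register: "The mean age of diagnosis is 9 years" (SD 4), mean age at LLT initiation is 11 years (SD 3) among the 57% who start, and mean follow-up is 2.9 years (SD 1.8).

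**The concern.** A reduction from the pre-treatment level and a difference from the earliest recorded follow-up agree only when the earliest value is also the value at LLT start. Otherwise the exposed child's change includes an untreated stretch, during which growth, puberty or lifestyle management may move LDL-C. Comparators' changes run from their own earliest values, over ages and durations that the plan does not align with those of the exposed.

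The affected quantity is the main clinical-effectiveness estimate. It is reported by age at initiation, which is the study question, and section 7.6 takes the LLT effect into the cost-effectiveness model as a proportional reduction. The choice of baseline therefore alters both the numerator and the denominator. Section 7.1 also repeats the LDL-C analyses in the primary care database (CPRD). Section 6.2 reports a mean of 3 LDL-C measures and a mean of 9 years of active follow-up in its feasibility sample, so an earliest value there could lie well before initiation.

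**Working it through.** **The plan's own figure.** The contrast in section 7.1 is 2.199 - 1.748 = 0.451 mmol/L (LLT begun before age 12 versus at 12 or older). With SD = sqrt((2.51² + 1.53²)/2) = 2.079, two-sided 0.05, 90% power and a 1.5:1 ratio:

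n(late) = (1.960 + 1.282)² × 2.079² × (1 + 1/1.5) / 0.451² = 372, and n(early) = 1.5 × 372 = 558.

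The plan states 376 and 560, so the calculation reproduces to within 3%. It does not depend on the present point. The 0.451 serves below only as a yardstick. The protocol calls the accompanying means (6.115 and 5.570) initial levels, without saying whether they are earliest or pre-start values.

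**What the definition does to a treated child.** Let Y0 be the earliest value, Yb the last value before or at LLT start, and Yf a later value. Then

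Y0 - Yf = (Yb - Yf) + (Y0 - Yb).

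The first term is the stated target and the second is untreated change. With constant untreated drift g per year and a gap of G years, the second term is -g × G. An untreated fall inflates the apparent reduction and an untreated rise deflates it.

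**When comparators remove it.** Suppose the treated child is followed T years after start and the comparator's change spans C years. With the same constant drift in both, the exposed-minus-comparator difference carries a residual of g × (G + T - C). This is zero if C = G + T. It is not zero in general, and a slope that varies with age adds to it. Nothing in the definition requires C = G + T or matching ages.

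**Effect on the early-late contrast.** Before any comparator is subtracted, the shift in early minus late reduction is g × (G_late - G_early). The documents give neither g nor the gaps by age at start, so all values of g and G here are assumptions.

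| Drift g (mmol/L per year) | Gap early / late (years) | Added to reduction, early / late | Shift in contrast | Share of 0.451 |
|---|---|---|---|---|
| -0.10 | 1 / 3 | +0.10 / +0.30 | -0.20 | -44% |
| -0.05 | 1 / 3 | +0.05 / +0.15 | -0.10 | -22% |
| +0.05 | 1 / 3 | -0.05 / -0.15 | +0.10 | +22% |
| +0.10 | 1 / 3 | -0.10 / -0.30 | +0.20 | +44% |
| -0.10 or +0.10 | 2 / 2 | equal | 0 | 0% |
| -0.10 | 3 / 1 | +0.30 / +0.10 | +0.20 | +44% |
| +0.10 | 3 / 1 | -0.30 / -0.10 | -0.20 | -44% |

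**Percentage scale.** If the printed means are taken as pre-start values, the ratios are 2.199/6.115 = 36.0% and 1.748/5.570 = 31.4%, a gap of 4.6 points. With g = -0.10 and gaps of 1 and 3 years they become 2.299/6.215 = 37.0% and 2.048/5.870 = 34.9%, a gap of 2.1 points. With g = +0.10 they become 2.099/6.015 = 34.9% and 1.448/5.270 = 27.5%, a gap of 7.4 points. These are ratios of means, for illustration only.

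**Whether the other methods repair it.** The weighting variables listed in section 7.1 and in the appendix include neither age nor LDL-C. E-values address unmeasured confounding, not the placing of the baseline.

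**The case against.** The strongest reply is that the plan names the pre-treatment level as its reference in several places and collects the LLT start date and pre-treatment LDL-C. On this reading the disputed clause exists mainly to give untreated children, who have no pre-treatment value, some definition of change. That reading is possible, and it is why the point is an inconsistency rather than a plan plainly fixed on diagnosis. But the clause as written governs the comparison of both groups, it appears twice, and it gives even the comparators no index age.

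Second, children unexposed up to a certain age may later start LLT, so a late starter's untreated years can count as unexposed time, and drift shared by both groups partly cancels. This stands as far as it goes: cancellation is complete only under matched ages and durations, which the plan does not require.

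Third, index visits and windows usually belong in a statistical analysis plan, which is not at hand. Silence would be no finding. Here the protocol fixes a definition that does not match its own target.

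A reader might go further and infer that the untreated years are credited to LLT, most of all in late starters. The documents do not support that. The 9 and 11 years are means over different groups (registered children and those who initiate), so the 2-year difference is not a paired interval. No gap by age at start is given, late starters may simply have been diagnosed late, and the sign depends on an unstated slope.

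**Conclusion.** The point holds as a mismatch between the stated target and the operational definition, together with a missing time zero for comparators. Followed literally, the definition puts untreated change into the exposed group's change wherever the earliest value precedes LLT start, with no assurance that the comparison removes it.

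Neither size nor direction can be derived from the documents. With drift of -0.10 to +0.10 mmol/L per year and gaps of 1 versus 3 years, all assumed, the early-late contrast moves by up to 0.20 of 0.451 mmol/L in either direction. It moves by zero if the gaps are equal, and reverses if early starters have the longer gap. These figures are taken before any cancellation by comparators. They show that the definition can matter for the age question, not that it biases the result by a known amount.

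**What to change.** Reconcile the target and the comparison wording in section 7.1, Analysis (a), and in the appendix's Clinical effectiveness analysis:

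- For treated children, define baseline as the last LDL-C before or at LLT start.
- For comparators, assign an index visit at a matching age while still untreated, and take baseline there.
- Measure change in both groups over the same follow-up intervals from that baseline.
- Include age and LDL-C at the index visit in the weights or the outcome model, and keep the earlier diagnosis value as a covariate. The last value before LLT may be the one that prompted prescribing, so an unadjusted start-anchored change would carry regression to the mean. These terms limit that.

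The cost is a change of analysis wording, since the start date, pre-treatment LDL-C and follow-up visit data are already sought. The downside is that children without a recent pre-start LDL-C would depend on the planned multiple imputation, with slightly wider intervals. Because this defines the main effectiveness estimate, it should be settled before the analysis is run.

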6.4.1 Protocol summary

Currently, treatment of paediatric FH remains secondary and tertiary care led. This study will collect questionnaire and interview data from HCPs currently involved in the clinical diagnosis and followup management of CYP with FH, in centres throughout the UK. It will provide data on and insight into current treatment practices in contemporary FH management in CYP, from lifestyle management to LLT, and from diagnosis to transfer to adult services. It will provide information on variation in clinical practice (routine practice/criteria on decisions to initiate LLT, treatment targets, adherence monitoring, starting dose, changing dose, and type/frequency of specialist healthcare provision) and the factors that influence this. Information will be used to describe the current clinical landscape and as variables in the PFHR analyses of clinical and cost-effectiveness, to account for clinical variation across sites in factors such as treatment targets.

There are no available estimates of the number of HCPs working in paediatric FH in the UK. Based on the existing PFHR clinical network and informal professional networks organised by the UK cholesterol charity HEART UK, we estimate 50-100 HCPs will complete questionnaires and we will interview 30 HCPs.

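### The protocol promises to account for site differences in LLT practice, but the stated confounder lists and outcome model do not carry this through, so between-site confounding of the starting-age effect may be only partly controlled

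*Protocol*

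**What the plan says.** **Expected variation.** Section 6.4, Protocol summary (the healthcare-professional study), lists the practice variation to be described: "routine practice/criteria on decisions to initiate LLT, treatment targets, adherence monitoring, starting dose, changing dose". It then says this information will serve "as variables in the PFHR analyses of clinical and cost-effectiveness, to account for clinical variation across sites in factors such as treatment targets".

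**Outcome model.** Section 7.1, Analysis (a): "A multi-level structure will be used to account for children being grouped at clinical sites, with site as a random effect". The Appendix, Clinical effectiveness analysis, says the same: "A multi-level structure will be used to account for patients being grouped at clinical sites, with site as a random effect". Neither gives site any other role.

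**Treatment weights.** The section 7.1 list runs "family history of CVD and/or FH in family, gender, genetic testing, body mass index (BMI), ethnicity, other health conditions", then "reasons for not being on LLT or non-adherence, process factors such as attendance frequency, and socioeconomic deprivation". The Appendix list adds smoking: "other health conditions, smoking status, socioeconomic deprivation". Neither names site or a site-practice variable.

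**Use of the questionnaire in section 7.1.** The healthcare-professional questionnaire appears there only as one of the things that will inform the E-value sensitivity analysis. Section 6.4 expects 50 to 100 completed questionnaires and does not state how many sites they will cover.

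**The concern.** Criteria for starting LLT drive the exposure: whether a child starts, at what age and at what LDL-C. Targets and dosing drive the LDL-C response. A site that differs from others in both respects is a common cause of exposure and outcome. A random intercept deals with clustering, but it assumes that the site effect is unrelated to the exposure. Where that fails, part of the site effect is reported as an effect of starting age.

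The E-value analysis is not the natural place for this, because it addresses unmeasured confounders and site is recorded for every child.

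The Analysis (a) estimates feed the economic model, which compares starting ages. Propagating their uncertainty does not remove bias. Analyses (b) and (c) and the cost analysis in Objective 5 take the same or a similar approach to confounding, so the gap would carry over to them.

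**Working it through.** **1. The plan's own figure.** Inputs from section 7.1: mean reductions 2.199 and 1.748, so the difference is 0.451 mmol/L; SDs 2.51 and 1.53; 90% power; alpha 0.05 (taken as two-sided); 60:40 allocation.

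- Common SD = √((2.51² + 1.53²)/2) = 2.079.
- Smaller group = (1 + 1/1.5) × (2.079 × (1.960 + 1.282)/0.451)² ≈ 372; larger group = 1.5 × 372 = 558.

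The plan states 376 and 560, so its figure reproduces. It serves here only as the yardstick of 0.451.

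**2. What a random intercept leaves behind, with no true age effect.** For equal sites of m initiators, let σ be the residual SD, τ the site SD of LDL-C response, s the site SD of starting age, w the within-site variance of starting age and ρ the site-level correlation. Then:

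- φ = σ²/(σ² + mτ²)
- W = w(m − 1)/m and B = s² + w/m
- bias per year = φρsτ/(W + φB)
- SE ratio, within-site to random-effect = √(1 + φB/W)

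Assumed, not in the documents: σ = 2.0, s = 1.0 to 1.5 years, τ = 0.2 to 0.5 mmol/L, ρ = −0.5. From section 6.1: starting age has mean 11 and SD 3, so w = 9 − s². A Normal(11, 3) cut at 12 has means 9.20 and 14.06, a gap of 4.86 years.

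| Setting | φ | Bias per year | × 4.86 (mmol/L, absolute) | Share of 0.451 |
|---|---|---|---|---|
| m = 24, s = 1.0, τ = 0.2 | 0.806 | −0.0806/(7.667 + 0.806×1.333) = −0.0092 | 0.045 | 10% |
| m = 24, s = 1.5, τ = 0.5 | 0.400 | −0.150/(6.469 + 0.400×2.531) = −0.0201 | 0.097 | 22% |
| m = 70, s = 1.0, τ = 0.2 | 0.588 | −0.0588/(7.886 + 0.588×1.114) = −0.0069 | 0.033 | 7% |
| m = 70, s = 1.5, τ = 0.5 | 0.186 | −0.0698/(6.654 + 0.186×2.346) = −0.0098 | 0.048 | 11% |

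Simulation on these assumptions (3,000 replicates per setting) agrees. With 39 sites of 20 to 35 initiators the bias is about 0.05 to 0.10 mmol/L, with p < 0.05 in 7 to 13% of replicates. With 11 sites of 70 it is 0.03 to 0.05. Within-site estimates are unbiased, with a standard error 4 to 17% larger. For comparison, the formula at m = 24, s = 1.5, τ = 0.2 gives √(1 + 0.806×2.531/6.469) = 1.147.

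**3. A less favourable set-up.** In a second simulation (1,000 replicates, residual SD 2.0, equal sites) one site factor drives both early starting (site SD 0.5 to 1.5 on the logit scale) and response (site SD 0.3 to 0.5 mmol/L). The true effect is again zero.

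| Sites × initiators | Bias with random intercept only (mmol/L) |
|---|---|
| 11 × 85 | 0.05 to 0.14 |
| 39 × 24 | 0.09 to 0.32 |
| 39 × 8 | 0.12 to 0.46 |

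With no site term at all the bias is 0.13 to 0.54. With site fixed effects, or a random intercept plus the site mean of exposure, it is within 0.02 of zero throughout.

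Both simulations are unweighted, without repeated measures.

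**The case against.** The strongest reply is that the plan already undertakes to deal with site practice. Section 6.4 says practice data will be used as variables in the Register analyses, and the questionnaire is directed at professionals who contribute to the Register and their contacts. A multi-level structure does not exclude site-level covariates, and the weight list has an open-ended item on process factors. The choice between fixed and random site effects is often left to the SAP, which is not at hand.

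Much of this stands. It would be wrong to say that the plan ignores site practice. What remains is that the sections of this protocol do not join up: one promises an adjustment that two explicit confounder lists omit. Nor is the questionnaire a secure substitute for site. It is completed once, is distributed and analysed in months 8 to 12, and comes with no promised coverage per site. It describes current practice, whereas the Register dates from 2012 and will add retrospective data.

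A reader might also infer from section 6.4 that early-starting sites treat harder. It does not say so; it expects variation in each aspect of practice and is silent on how they correlate. The bias needs that correlation, and every value used above is assumed.

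The number of sites matters too. The 39 sites describe the Register up to 2019. The Appendix starts with 6 sites, and section 6.1.1 names about 11 key sites, although others may join. The lower figures may therefore be closer to the study as it will run. The 0.46 comes from 39 sites of 8, about 312 initiators against the 936 in the sample-size statement.

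**Conclusion.** The point holds as an inconsistency with a plausible risk of bias. Followed as written, section 7.1 leaves a recorded, plausible confounder only partly controlled, although section 6.4 undertakes to account for it.

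Its size cannot be settled from the documents, which give neither a between-site variance nor a correlation. Under the assumed values the residual bias is about 0.03 to 0.10 mmol/L in one simulation (roughly 7 to 22% of 0.451) and 0.05 to 0.46 in the other, and it is smaller with few large sites.

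The stronger reading, that the planned starting-age estimate is biased and must be replaced by a within-site one, is not supported. It would require that sites starting earlier treat more intensively and that the promised practice variables never reach the model. The documents establish neither.

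**What to change.** - **Reconcile the text.** Make section 6.4 (Protocol summary), section 7.1 Analysis (a) and the Appendix analysis section agree on how site practice enters the analysis.
- **Outcome model.** Add site means of age and LDL-C at initiation beside the site random effect, or use site fixed effects. Report the within-site estimate next to the planned one and carry it into the economic model at least as a scenario.
- **Weights.** Name site, with small sites grouped, or the section 6.4 practice variables among the confounders where overlap allows.

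The cost is some wording and a few model terms built from data already recorded. The standard error grows by about 4 to 17% in the unweighted simulation; the cost under weighting was not tested. Separate indicators for every small site in the weight model should not be required. The existing Register averages 613/39 ≈ 16 children per site, and at 57% initiating LLT that is about 9 initiators per site, few enough to make weights unstable. Grouping small sites avoids this but leaves some confounding within the groups.
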